  - Subjects without active disease in the last 5 years may be considered for enrollment after discussion with the sponsor-investigator
  - Subjects with celiac disease controlled by diet alone may be considered for enrollment after discussion with the sponsor-investigator
11. QT interval corrected for heart rate using Fridericia's formula (QTcF)  $\geq 470$  ms calculated. Any clinically significant abnormalities detected require triplicate ECG results and a mean QTcF  $< 470$  ms calculated from 3 ECGs obtained over a brief period (eg, 30 minutes)
12. Past medical history of Interstitial Lung Disease (ILD), drug-induced ILD, radiation pneumonitis which required steroid treatment, or any evidence of clinically active interstitial lung disease.
13. History of active primary immunodeficiency

14. Active infection, including tuberculosis (clinical evaluation that includes clinical history, physical examination and radiographic findings, and tuberculosis testing in line with local practice), hepatitis B, hepatitis C, or human immunodeficiency virus (HIV, positive HIV 1 or 2 antibodies). Active hepatitis B virus (HBV) infection is defined by a positive HBV surface antigen (HBsAg) result. Subjects with a past or resolved HBV infection (defined as the presence of hepatitis B core IgG antibody and the absence of HBsAg, deoxyribonucleic acid [DNA] negative) are eligible. Subjects positive for hepatitis C virus (HCV) antibody are eligible only if polymerase chain reaction is negative for HCV ribonucleic acid (RNA).
15. Current or prior use of immunosuppressive medication within 14 days before the first dose of tremelimumab. The following are exceptions to this criterion:
  - Intranasal, inhaled, topical steroids, or local steroid injections (eg, intra-articular injection)
  - Systemic corticosteroids at physiologic doses not to exceed 10 mg/day of prednisone or its equivalent
  - Steroids as premedication for hypersensitivity reactions (eg, CT scan premedication)
16. Receipt of live attenuated vaccine within 30 days prior to the first dose of study treatment.  
**NOTE:** Subjects, if enrolled, should not receive live vaccine during the study and up to 30 days after the last dose of tremelimumab.
17. Known allergy or hypersensitivity to tremelimumab or any investigation product excipient, or to other humanized mAbs
18. Weight  $\leq 35$  kg

### **3.3 Re-Treatment with Tremelimumab Criteria**

#### **Inclusion Criteria**

1. ECOG Performance Status of 0 or 1 within 14 days prior to re-treatment.
2. Demonstrate adequate organ function as defined below. All labs to be obtained within 14 days prior to re-treatment.
  - Absolute Neutrophil Count (ANC):  $\geq 1500/\text{mm}^3$
  - Hemoglobin (Hgb):  $\geq 9 \text{ g/dL}$
  - CrCl or creatinine:  $\geq 30 \text{ cc/min}$  or creatinine  $\leq 1.5$
  - AST and ALT:  $\leq 2.5 \times \text{ULN}$  ( $\leq 5 \times \text{ULN}$  for subjects with hepatic metastases)  
Cockcroft-Gault formula will be used to calculate creatinine clearance or 24 urine collection for creatinine can be utilized
3. Evidence of postmenopausal status or negative urinary or serum pregnancy test for female premenopausal subjects prior to re-treatment.
4. Females of childbearing potential who are sexually active with a non-sterilized male partner must be willing to abstain from heterosexual activity or to use 1 highly effective method of

contraception from the time of informed consent until 90 days after the last dose of tremelimumab. Non-sterilized male partners of a female patient must use male condom plus spermicide throughout this period.

5. Non-sterilized males who are sexually active with a female partner of childbearing potential must use a male condom plus spermicide from screening through 90 days after receipt of the final dose of tremelimumab. Female partners (of childbearing potential) of male subjects must also use a highly effective method of contraception throughout this period.
6. Must have life expectancy of  $\geq 12$  weeks.

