| Bilirubin  | $\leq 1.5 \times$ upper limit of normal (ULN)
This will not apply to subjects with confirmed Gilbert's syndrome (persistent or recurrent hyperbilirubinemia [predominantly unconjugated bilirubin] in the absence of evidence of hemolysis or hepatic pathology), who may be considered for enrollment after discussion with the Sponsor Investigator |
| Aspartate aminotransferase (AST)                           | $\leq 2.5 \times$ ULN ( $\leq 5 \times$ ULN for subjects with hepatic metastases)  |
| Alanine aminotransferase (ALT)                             | $\leq 2.5 \times$ ULN ( $\leq 5 \times$ ULN for subjects with hepatic metastases)  |

1 Cockcroft-Gault formula will be used to calculate creatinine clearance or 24 urine collection for creatinine can be utilized

11. Evidence of postmenopausal status or negative urinary or serum pregnancy test for female premenopausal subjects. Women will be considered postmenopausal if they have been amenorrheic for 12 months without an alternative medical cause. The following age-specific requirements apply:
  - Women < 50 years of age would be considered postmenopausal if they have been amenorrheic for 12 months or more following cessation of exogenous hormonal treatments and if they have luteinizing hormone and follicle-stimulating hormone levels in the postmenopausal range for the institution or underwent surgical sterilization (bilateral oophorectomy, bilateral salpingectomy, or hysterectomy).
  - Women ≥ 50 years of age would be considered postmenopausal if they have been amenorrheic for 12 months or more following cessation of all exogenous hormonal treatments, had radiation-induced oophorectomy with last menses >1 year ago, had chemotherapy-induced menopause with >1 year interval since last menses, or underwent surgical sterilization (bilateral oophorectomy, bilateral salpingectomy, or hysterectomy)
12. Females of childbearing potential who are sexually active with a non-sterilized male partner must be willing to abstain from heterosexual activity or to use 1 highly effective method of contraception from the time of informed consent until 90 days after the last dose of tremelimumab. Non-sterilized male partners of a female patient must use male condom plus spermicide throughout this period. See Table 2 for acceptable contraceptive methods.

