### **5.1.3 Re-treatment of Subjects Progressing within 1 Year of Completing Initial Tremelimumab**

Patients that complete the initial 7 cycles of tremelimumab then have evidence of disease progression per RECIST 1.1 (with or without confirmation) during the 1-year follow-up period may be eligible for re-treatment with up to 7 additional cycles of tremelimumab. Such patients are required to meet the eligibility criteria outlined in Section 3.3. Testing done during progression may be used for screening prior to re-treatment. Subjects should follow the same schedule of events/procedures for the initial Cycles 1-7 of tremelimumab.

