## 6.2 Dose Delays/Dose Modifications

The following general guidance should be followed for management of tremelimumab-related toxicities.

- Treat each of the toxicities with maximum supportive care (including holding the agent suspected of causing the toxicity if required).
- If the symptoms promptly resolve with supportive care, consideration should be given to continuing study drug along with appropriate continuing supportive care.
- If medically appropriate, dose modifications are permitted (Appendix 1)
- All dose modifications should be documented with clear reasoning and documentation of the approach taken.

Guidelines for the management of immune-mediated reactions, infusion-related reactions, and non-immune-mediated reactions are provided in Appendix 1, Dosing Modification and Toxicity Management Guidelines. In addition, there are certain circumstances in which tremelimumab should be permanently discontinued (see Section 6.4 and Appendix 1).

Following the first dose of study drug, subsequent administration tremelimumab can be modified based on toxicities observed as described in Appendix 1, the Dosing Modification and Toxicity Management Guidelines. These guidelines apply to adverse events considered by the reporting site investigator to be causally related to tremelimumab. In case of doubt, the site investigator should consult with the sponsor-investigator.

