| Tremelimumab                                  |                 | X  (750 mg)                |  |   |                                  |                           |   |
| SPECIMEN COLLECTION                                |                 |  |  |   |                                  |                           |   |
| Archival Tumor Tissue or Fresh Biopsy        | X  |  |  |   |                                  |                           |   |
| Tumor tissue obtained for clinical purposes  | X  | X                         |  | X                          | X                   | X            | X                                  |
| Blood samples                                | X  | X                         |  |   |                                  | X            | X                                  |
| Stool sample for microbiome                  |                 | X                         |  |   |                                  |                           |   |
| FOLLOW-UP  |                 |  |  |   |                                  |                           |   |
| Survival Status, Subsequent Therapy                       |                 |  |  |   | X                                |                           |   |

CBC with differential and platelet to include: Hgb, Hct, WBC, ANC, absolute lymphocyte count, platelets. CMP to include sodium, potassium, chloride, creatinine, blood urea nitrogen; liver function tests (LFTs) to include AST, ALT, total bilirubin, alkaline phosphatase

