| 
Drug administration modifications of study drug/study regimen will be made to manage potential immune-related AEs based on severity of treatment-emergent toxicities graded per NCI CTCAE v4.03.
 
In addition to the criteria for permanent discontinuation of study drug/study regimen based on CTC grade/severity (table below), permanently discontinue study drug/study regimen for the following conditions:
 
 
• Inability to reduce corticosteroid to a dose of <math>\leq 10</math> mg of prednisone per day (or equivalent) within 12 weeks after last dose of study drug/study regimen
 
• Recurrence of a previously experienced Grade 3 treatment-related AE following resumption of dosing
 
 
Grade 1      No dose modification
 
Grade 2      Hold study drug/study regimen dose until Grade 2 resolution to Grade <math>\leq 1</math>.
 
If toxicity worsens, then treat as Grade 3 or Grade 4.
 
Study drug/study regimen can be resumed once event stabilizes to Grade <math>\leq 1</math> after completion of steroid taper.
 
Patients with endocrinopathies who may require prolonged or continued steroid replacement can be retreated with study drug/study regimen on the following conditions:
 
 
1. The event stabilizes and is controlled.
 
2. The patient is clinically stable as per Investigator or treating physician's clinical judgement.
 
3. Doses of prednisone are at <math>\leq 10</math> mg/day or equivalent.
 
 | 
It is recommended that management of immune-mediated adverse events (imAEs) follows the guidelines presented in this table:
 
 
– It is possible that events with an inflammatory or immune mediated mechanism could occur in nearly all organs, some of them not noted specifically in these guidelines.
 
– Whether specific immune-mediated events (and/or laboratory indicators of such events) are noted in these guidelines or not, patients should be thoroughly evaluated to rule out any alternative etiology (e.g., disease progression, concomitant medications, and infections) to a possible immune-mediated event. In the absence of a clear alternative etiology, all such events should be managed as if they were immune related. General recommendations follow.
 
– Symptomatic and topical therapy should be considered for low-grade (Grade 1 or 2, unless otherwise specified) events.
 
– For persistent (<math>>3</math> to 5 days) low-grade (Grade 2) or severe (Grade <math>\geq 3</math>) events, promptly start prednisone 1 to 2 mg/kg/day PO or IV equivalent.
 
– Some events with high likelihood for morbidity and/or mortality – e.g., myo-carditis, or other similar events even if they are not currently noted in the guidelines – should progress rapidly to high dose IV corticosteroids (methylprednisolone at 2 to 4 mg/kg/day) even if the event is Grade 2, and if clinical suspicion is high and/or there has been clinical confirmation. Consider, as necessary, discussing with the study physician, and promptly pursue specialist consultation.
 
– If symptoms recur or worsen during corticosteroid tapering (28 days of taper), increase the corticosteroid dose (prednisone dose [e.g., up to 2 to 4 mg/kg/day PO or IV equivalent]) until stabilization or improvement of symptoms, then resume corticosteroid tapering at a slower rate (<math>>28</math> days of taper).
 
– More potent immunosuppressives such as TNF inhibitors (e.g., infliximab) (also refer to the individual sections of the imAEs for specific type of immunosuppressive) should be considered for events not responding to systemic steroids. Progression to use of more potent immunosuppressives should proceed more rapidly in events with high likelihood for morbidity and/or mortality – e.g., myocarditis, or other similar events even if they are not currently noted in the guidelines – when these events are not responding to systemic steroids.
 
– With long-term steroid and other immunosuppressive use, consider need for Pneumocystis jirovecii pneumonia (PJP, formerly known as Pneumocystis carinii pneumonia) prophylaxis, gastrointestinal protection, and glucose monitoring.
 
 |

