| Grade 3 or 4
(Grade 3 diarrhea: stool frequency of $\geq 7$ over baseline per day;
Grade 4 diarrhea: life threatening consequences)
(Grade 3 colitis: severe abdominal pain, change in bowel habits, medi-cal intervention indicated, peritoneal signs;
Grade 4 colitis: life-threatening consequences, urgent intervention indicated) | Grade 3
Permanently discontinue study drug/study regimen for Grade 3 if toxicity does not improve to Grade $\leq 1$ within 14 days; study drug/study regimen can be resumed after completion of steroid taper.

Grade 4
Permanently discontinue study drug/study regimen.    | For Grade 3 or 4:
– Promptly initiate empiric IV methylprednisolone 2 to 4 mg/kg/day or equivalent.
– Monitor stool frequency and volume and maintain hydration.
– Urgent GI consult and imaging and/or colonoscopy as appropriate.
– If still no improvement within 3 to 5 days of IV methylprednisolone 2 to 4 mg/kg/day or equivalent, promptly start further immunosuppressives (e.g., infliximab at 5 mg/kg once every 2 weeks). Caution: Ensure GI consult to rule out bowel perforation and refer to infliximab label for general guidance before using infliximab.
– Once the patient is improving, gradually taper steroids over $\geq 28$ days and consider prophylactic antibiotics, antifungals, and anti-PJP treatment (refer to current NCCN guidelines for treatment of cancer-related infections [Category 2B recommendation]). a |
| Hepatitis (elevated LFTs)

Infliximab should not be used for management of immune-related hepatitis.   | Any Grade

General Guidance  | For Any Grade:
– Monitor and evaluate liver function test: AST, ALT, ALP, and TB.
– Evaluate for alternative etiologies (e.g., viral hepatitis, disease progression, concomitant medications).   |
| Grade 1
(AST or ALT $>$ ULN and $\leq 3.0 \times$ ULN and/or TB $>$ ULN and $\leq 1.5 \times$ ULN)  | 
 
• No dose modifications.
 
• If it worsens, then treat as Grade 2 event.
 
  | For Grade 1:
– Continue LFT monitoring per protocol.  |

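### The re-treatment criteria in Section 3.3 repeat every organ-function limit from first entry except bilirubin, leaving no cut-off for a rise attributed to a cause other than the drug

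*Combined protocol and SAP*

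**What the plan says.** Section 3.1 item 10 sets six laboratory limits for first entry: ANC, haemoglobin, creatinine clearance or creatinine, bilirubin, AST and ALT. The bilirubin limit is 1.5 × ULN. Confirmed Gilbert's syndrome is excepted, after discussion with the sponsor-investigator.

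Section 3.3 item 2 governs a second course: "Demonstrate adequate organ function as defined below. All labs to be obtained within 14 days prior to re-treatment". The list that follows has no bilirubin entry.

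Section 5.1.3 names Section 3.3 as the gate: "Such patients are required to meet the eligibility criteria outlined in Section 3.3". Footnote 17 to the Section 7 calendar says the same. Neither brings the Section 3.1 limits back in.

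On managing liver abnormalities once a patient is on drug, Section 6.2 says of Appendix 1: "These guidelines apply to adverse events considered by the reporting site investigator to be causally related to tremelimumab". The general part of Appendix 1 widens this a little: "In the absence of a clear alternative etiology, all such events should be managed as if they were immune related".

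**The concern.** The sponsor judged a bilirubin limit necessary before a first dose, and the plan gives no reason for dropping it before an eighth. It is the only one of the six limits to disappear.

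The patients concerned are those in whom it could matter. To be considered for re-treatment a patient must have completed seven cycles and then progressed during the following year. Appendix 1, under hepatitis, names disease progression as an alternative cause of abnormal liver tests. If progression is in the liver or obstructs the bile ducts, bilirubin can rise for a reason that the toxicity rules do not govern.

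What is at stake is patient safety. Section 10.1.4 lists hepatitis and liver enzyme elevations among the risks of tremelimumab. A patient who starts the second course with bilirubin above 1.5 × ULN is already in or above the range that Appendix 1 grades as Grade 2, so a later drug-related rise is harder to recognise. Appendix 1 also lets dosing resume after some liver events at Grade 1 or baseline. The plan does not say whether baseline means the value at re-treatment; if it does, a raised starting value would loosen that rule too.

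**Working it through.** **Step 1. Compare the two lists.**

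| Item | Section 3.1, first entry | Section 3.3, re-treatment |
|---|---|---|
| ANC | ≥ 1500/mm³ | same |
| Haemoglobin | ≥ 9 g/dL | same |
| CrCl or creatinine | ≥ 30 cc/min or ≤ 1.5 | same |
| Bilirubin | ≤ 1.5 × ULN, Gilbert's excepted | absent |
| AST | ≤ 2.5 × ULN (≤ 5 × with hepatic metastases) | same |
| ALT | ≤ 2.5 × ULN (≤ 5 × with hepatic metastases) | same |

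Six limits at first entry, five at re-treatment: 6 − 5 = 1 missing. The list in Section 3.3 is intact and even keeps the Cockcroft-Gault note from the Section 3.1 table, so this does not look like a redaction or a damaged table.

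**Step 2. Look for another rule that would bind on a bilirubin rise with an identified non-drug cause.**

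- *Appendix 1, hepatitis.* Hold drug above 1.5 × ULN; discontinue above 5 × ULN. Under Section 6.2 and the general part of Appendix 1, this applies to events that are drug-related or have no clear other cause.
- *Appendix 1, Hy's law.* Permanent discontinuation, but only where no other cause is present.
- *Section 6.3.* Needs AST or ALT ≥ 3 × ULN together with bilirubin ≥ 2 × ULN, then refers back to Appendix 1 and deals with SAE reporting. It sets no eligibility limit.
- *Section 7, footnote 16.* Liver tests must be reviewed within 3 days before dosing. No cut-off is given.
- *Section 3.3, exclusion 1.* Concerns toxicities, without a laboratory figure.

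Bilirubin cut-offs found for this case: none.

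**Step 3. A concrete case.** Take a patient whose tumour has progressed and obstructs the bile duct, with AST and ALT below 2.5 × ULN and bilirubin 4 × ULN. Section 3.1 would refuse entry (4 > 1.5). Section 3.3 passes the patient on every listed laboratory value. Section 6.3 is not triggered, because AST and ALT are below 3 × ULN. Appendix 1 does not require a hold, because the cause is identified and is not the drug. The further exposure allowed is up to 7 × 750 mg = 5,250 mg.

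**Step 4. How many patients.** The plan gives no expected number of re-treated patients, so both inputs are assumptions: n = 1 to 6 re-treated out of 28, and a proportion p = 0.02 to 0.10 of those with bilirubin above 1.5 × ULN from a non-drug cause. The expected number is n × p, and the chance of at least one case is 1 − (1 − p)ⁿ.

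| n | p | Expected number | Chance of at least one |
|---|---|---|---|
| 1 | 0.02 | 0.02 | 1 − 0.98 = 0.02 |
| 3 | 0.05 | 0.15 | 1 − 0.95³ = 0.14 |
| 6 | 0.10 | 0.60 | 1 − 0.90⁶ = 0.47 |

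**Step 5. Effect on the primary analysis.** Section 9.4.5 counts response only until progression. Re-treatment begins after progression, so the response rate and the Simon design are unaffected.

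**The case against.** The best reply is that the patient is not unprotected in practice. Re-treatment is permitted, not owed. The candidate must have ECOG 0 or 1, a life expectancy of at least 12 weeks and capped AST and ALT. A physician sees the liver tests before dosing, and Section 6.4 lets the investigator stop whenever a change of therapy is in the patient's interest. A jaundiced patient with serious hepatic progression would have to get past all of that. This stands as a reason to expect few cases, but each of these checks rests on judgement or on something other than bilirubin. The plan thought a number necessary at first entry, where the same kinds of judgement were also available.

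Section 6.3 narrows the gap: its trigger has no attribution test, and some patients with hepatic metastases would meet it. It does not reach a bilirubin rise with AST and ALT below 3 × ULN, and it leads back to Appendix 1.

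A further point is that the plan already accepts AST and ALT up to 5 × ULN with hepatic metastases, which is within Appendix 1 Grade 2, and that a tumour-related bilirubin rise during the first seven cycles has no mandatory cut-off either. Both are true. The first weakens the argument about recognising later toxicity, though that allowance was made for transaminases and deliberately not for bilirubin. The second concerns continuing a course already under way, whereas Section 3.3 is an eligibility screen for starting a new one.

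Some other Section 3.3 criteria are shorter than their first-entry counterparts, so deliberate relaxation cannot be ruled out. If it was deliberate, the plan should say so.

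**Conclusion.** The concern holds. Section 3.3 omits the bilirubin limit, Section 3.3 is the only stated gate for re-treatment, and no other rule supplies a cut-off when the rise is attributed to something other than tremelimumab. Rises that are drug-related or unexplained remain covered by Appendix 1.

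The consequence is small in number: an expected 0.02 to 0.6 patients. That range, and the probabilities with it, rests wholly on the assumed re-treatment count and proportion; the upper end needs both assumptions at their extremes. The documents give no evidence on how much extra hazard tremelimumab carries in a patient whose bilirubin is raised for another reason. This is a safety and eligibility gap that should be corrected because doing so is cheap. It does not threaten the trial's conclusions.

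**What to change.** Add one line to Section 3.3 item 2: bilirubin ≤ 1.5 × ULN, with the Section 3.1 exception for confirmed Gilbert's syndrome after discussion with the sponsor-investigator.

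No new test is needed. The Section 7 calendar already schedules the metabolic profile at re-treatment screening, and its key defines the "liver function tests (LFTs) to include AST, ALT, total bilirubin, alkaline phosphatase". Sample size and analysis do not change. The cost is that an occasional patient may become ineligible for re-treatment, one whose bilirubin would also have failed the first-entry limit.
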